Symptoms are subjective experiences self-reported by the patient, and are a subset of patient perceptions of health status and HRQoL (21). HRQoL is a multidimensional construct of diverse functional scales (e.g. physical function, psychological function, social role function) and symptom scales (e.g. disease-related or treatment-related symptoms) (21).

Three questionnaires were selected and are described in the next paragraphs.

a) EQ-5D-5L

The EQ-5D-5L is a generic preference-based measure of health status, which is the most commonly used tool used to derive utility values that can be utilized within an economic evaluation model (22). This tool is also commonly used in lung cancer trials (23). It includes questions covering five domains: mobility, self-care, usual activities, pain and discomfort, and anxiety and depression. For each domain, 5-level questions are posed. Additionally, patients are asked to fill in how they feel today on a vertical visual analogue scale (VAS). Validated versions are available for paper-based and via smartphones and tablet administration.

The questionnaire will be administered at baseline, every 3 ± 1 weeks to take into account that visit intervals may vary between patients and across therapies (in this way the completion of the questionnaire will happen approximately 1 day before each cycle of treatment for chemotherapy patients), and at the end of the study period. This frequency of administration is in line with other trials involving lung cancer patients that administered the EQ-5D (24, 25).

b) FACT-L (lung cancer module):

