Assuming a constant recruitment rate of 6 patients per week (2 patients per centre) the study is planned to recruit consecutively for 26 weeks (Figure 9).

Figure 9 - Planned recruitment process

Randomization

Randomization services will be provided by AdvicePharma via a computer system using randomly permuted blocks and stratified by trial centers and therapy (i.e.

chemotherapy, immunotherapy and biological therapy). Nurses or physicians involved in the study will take care of the enrollment phase. After signature of informed consent, a randomization code will be generated electronically and assigned to the patient. During the informed consent procedure, the team will go carefully through the different aspects of the study design and will present LuCApp as well as the usual care alternative. During this phase the patient will have an opportunity to discuss her level of experience with mobile technology.

The study is nonblinded, in fact it is not possible to blind the participants when this type of intervention and these outcomes are under investigation.

Participants will remain on study until discontinuation of cancer treatment, voluntary withdrawal, study termination or death.

Statistical methods

The baseline differences between the intervention and control groups will be assessed using the chi-square (χ^2) test for binary demographic data and the independent sample t-test for continuous variables. We will summarize graphically and numerically the distributions of symptoms, outcomes as well as covariates.

For the primary quality of life endpoint, two groups t-test will be used to compare changes from baseline in FACT-L in the experimental group and the control group 12 weeks after randomization. A multivariable linear regression model, with change score as the dependent variable, adjusted for covariates will be fitted. The proportion of patients in each arm who experienced improved, unchanged, or worsened scores from baseline will be compared using χ^2 or Fisher's exact test. This analysis will be run for both any change and clinically meaningful changes for specific subscales (51). The analyses will be repeated at 24 weeks after randomization.

For all other questionnaires, changes from baseline in the LuCApp group and the control group at 12 and 24 weeks after randomization will be computed using t-test comparison. The SCNS-SF34, usability and ZBI data results will be summarized graphically and numerically.

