As a secondary analysis, adjusting for possible confounding factors of demographic variables and clustering in centers, the repeated measures multivariate analysis of covariance will be conducted to determine whether LuCApp affects HRQoL and symptoms as measured via EQ-5D-5L, FACT-L and HADS at different time points of

data collection. Additionally, mixed-effects models will be used to analyze the same subject-specific continuous outcomes with incorporation of terms for intervention, time, centers, and any identified covariates.

Analysis of missing data will first determine how common a problem this is and whether it can be assumed to be missing at random or not missing at random. Multiple sensitivity imputation analyses will be conducted, including last observation carried forward, minimum observation values carried forward, average observation values carried forward, and multiple imputation. EQ-5D value will be set to zero if death occurs before 6 months. Survival time will be calculated from the date of enrollment to the date of death or censoring those alive at the last follow-up with the use of the Kaplan–Meier method. A Cox proportional-hazards model will be fitted to assess the effect of LuCApp on survival, with adjustment for demographic characteristics and baseline performance status.

By combining EQ-5D derived utilities and survival quality-adjusted life years (QALY) for participants in both arms will be computed and compared using two group t-tests between LuCApp and standard care arm. A multivariable linear regression model with QALY as dependent variable will be used to adjust for other covariates. Resource consumption and related costs will be calculated and reported for each treatment group and compared by means of parametric and non-parametric tests (52).

Two-sided P values of less than .05 were considered to indicate statistical significance. All statistical analyses will be performed using STATA® 14.2, StataCorp, Texas.

Ethics & Informed Consent

All procedures involved in the study were consistent with generally accepted standards of ethical practice. The protocol is submitted for ethical clearance to the ethical committees at the three sites involved in the RCT (full list of participating centers is available as an attachment).

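### The QALY comparison is an unadjusted t-test followed by a regression with unnamed covariates. Baseline EQ-5D utility is named in neither, and neither is designated the main result.

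*Combined protocol and SAP*

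**What the plan says.** - **Unadjusted comparison** (Statistical methods): QALYs are built from EQ-5D utilities and survival, and "will be computed and compared using two group t-tests between LuCApp and standard care arm".
- **Adjusted comparison** (next sentence): "A multivariable linear regression model with QALY as dependent variable will be used to adjust for other covariates". No covariate is listed. The Cox model in the same section does have a named adjustment set: demographic characteristics and baseline performance status.
- **Availability of baseline utility** (Outcomes, EQ-5D-5L): "The questionnaire will be administered at baseline, every 3 ± 1 weeks", and again at the end of the study.
- **Other uses of baseline scores** (Statistical methods): "For all other questionnaires, changes from baseline in the LuCApp group and the control group at 12 and 24 weeks" are compared by t-test. This covers the EQ-5D-5L as a questionnaire. The repeated-measures analysis of EQ-5D-5L, FACT-L and HADS is described as "adjusting for possible confounding factors of demographic variables and clustering in centers". Neither statement concerns the QALY.
- **Balance by design** (Randomization): allocation is "stratified by trial centers and therapy". Baseline utility is not a stratification factor.
- **Deaths** (Statistical methods): "EQ-5D value will be set to zero if death occurs before 6 months".

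**The concern.** A QALY over 24 weeks is the area under the utility curve, and that curve starts at the baseline value. The total therefore contains baseline utility and is correlated with it through every later visit. The questionnaire scores are analysed as changes, which brings the baseline in. A QALY total is not a change, so its t-test has no baseline term at all.

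The regression could supply that term, but a reader cannot tell whether it will. The plan also tests the arms for baseline differences and leaves the QALY covariates open, so the adjustment could be chosen after those differences have been seen.

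Two things are at stake: precision, and how to read the result if the arms happen to differ in utility at the start. Both matter more when the horizon is short, because the QALY differences that can be reached are then small.

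**Working it through.** **The plan's own figure.** The documents state no sample size, SD, effect or power for QALYs or utility. The only design figure to reproduce is the 120 evaluable patients for the TOI (Sample size: difference 6, SD 11.54, 80% power, two-sided 0.05). The normal approximation gives 59 per arm (118 in total). The t-based calculation gives 59.05 per arm, so 60 per arm (120 in total). The figure reproduces, and 60 per arm is used below.

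**Inputs**
- From the documents: 60 per arm; horizon 24/52 = 0.4615 years.
- Assumed: utility SD 0.20 to 0.25; slope of later utility on baseline 0.5 to 0.7; a benchmark utility gain of 0.05; no deaths.

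**Step 1: chance imbalance at baseline.** Standard error of the baseline difference = SD × √(2/n).
- SD 0.20: 0.20 × √(2/60) = 0.0365
- SD 0.25: 0.25 × √(2/60) = 0.0456

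**Step 2: carry-over into the QALY difference.** Shift = imbalance × slope × 24/52.
- Low end: 0.0365 × 0.5 × 0.4615 = 0.0084
- High end: 0.0456 × 0.7 × 0.4615 = 0.0147

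**Step 3: benchmark.** 0.05 × 0.4615 = 0.0231 QALY. The shift is 0.0084/0.0231 = 0.36 to 0.0147/0.0231 = 0.64 of that.

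**Step 4: the area calculated directly.** Take a trapezoid area with visits every three weeks, SD 0.20, equal correlation between all visits, and no deaths. The shift is for a baseline imbalance of 0.05. The standard errors are for the QALY difference with 60 per arm.

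| Correlation between visits | Shift (QALY) | SE, t-test | SE, adjusted for baseline | Variance reduction |
|---|---|---|---|---|
| 0.3 | 0.008 | 0.0104 | 0.0087 | 31% |
| 0.5 | 0.012 | 0.0126 | 0.0089 | 51% |
| 0.7 | 0.017 | 0.0144 | 0.0079 | 70% |

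The ceiling is 0.023, reached only if the imbalance persists in full. If the correlation instead decays from visit to visit (0.80 to 0.95 per three-week step), the shift is 0.011 to 0.019.

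**Step 5: error rate.** Simulation under no effect, 4,000 runs, SD 0.20, correlation 0.5, 60 per arm.

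| Runs | t-test rejects | Baseline-adjusted rejects |
|---|---|---|
| All | 4.9% | 5.2% |
| Absolute imbalance above 0.05 (17% of runs) | 16.8% | 4.5% |

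**Step 6: deaths.** Assume 10% to 30% deaths, unrelated to arm or baseline and scored as zero, with SD 0.20 to 0.25 and visit correlation 0.5 to 0.7. The variance reduction falls to roughly 14% to 47%. The shift for a one-standard-error imbalance stays near 0.007 to 0.013.

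**The case against.** The strongest reply is that randomisation already protects the t-test. Its standard error includes the variation due to baseline, and it holds its level over all randomisations (4.9% in the simulation). That stands. A reader might infer that the planned test is biased or invalid, and it is not. What remains is lower precision, and a conditional bias in those trials where the arms start apart.

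Other stronger readings also fail:
- **That the regression leaves out baseline utility.** The text neither names nor excludes it. What can be said is that the covariates are not pre-specified.
- **That baseline EQ-5D is collected and never used.** It enters the change-score analysis of the questionnaire. It is unnamed only in the QALY analysis.
- **That an imbalance passes in full into the QALY difference.** That would need complete persistence. The carry-over is scaled by the horizon and by the correlation with later utility.
- **That a cost-effectiveness decision hangs on this.** The trial is described as a feasibility and pilot study, cost-effectiveness is to be explored, the primary outcome is TOI change at 12 weeks, and no cost-effectiveness threshold or adoption rule is given.

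It is also fair to object that the magnitudes rest on values from outside the documents. With a benchmark gain of 0.10 instead of 0.05, the ratios in step 3 halve. Deaths make any single figure for the precision gain unreliable.

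**Conclusion.** The point holds in a limited form. The one QALY comparison that is fully specified has no baseline term, the regression that could supply one has no listed covariates, and neither is ranked as the main result. Because baseline utility is collected and is part of the QALY, a baseline-adjusted comparison is a concrete improvement on the stated t-test, and more than a request for missing detail.

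On the assumed inputs, an ordinary imbalance of one standard error moves the unadjusted difference by about 0.008 to 0.015 QALY, against 0.023 for the assumed benchmark gain. The shift changes little when deaths are scored as zero. The precision gain does change: it runs from about 31% to 70% of the variance with no deaths (visit correlation 0.3 to 0.7) and is clearly smaller with them. Since QALYs are secondary and exploratory here, this is a free improvement and does not threaten the trial's main conclusion.

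**What to change.** In Statistical methods, replace the two QALY sentences with a statement that:
- the main QALY comparison is a linear regression of QALY on arm, baseline EQ-5D utility, centre and therapy, the last two being the stratification factors;
- the unadjusted two-group t-test is reported as a supplement;
- any further covariates are listed before the data are seen.

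The cost is a sentence or two. All the data are already collected, and neither the sample size nor the visit schedule changes.

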Usual care will consist of standard procedures currently available at participating centers for monitoring and documenting symptoms. These therapeutical procedures are based on the guidelines developed by the National Comprehensive Cancer Network (NCCN) and the Associazione Italiana di Oncologia Medica (AIOM) (20). Symptoms for control arm patients will be discussed and registered during scheduled clinical visits

with the oncologists. Standard-of-care patients will fill out their PROMs following the same schedule identified for LuCApp patients with paper questionnaires during clinic visits, or at home (having received paper questionnaires during the previous visit) or via telephonic interviews with the research team. Patients are usually allowed to contact their relative sites for concerning symptoms that occur between scheduled visits or advised to see the out-of-hour doctor or the emergency department if needed. This option is also recommended for the intervention arm during weekends.

Outcomes

As discussed above, the overarching research question of this study is to explore and pilot the impact of using LuCApp on relevant outcomes in patients with lung cancer. LuCApp has several functionalities and this pilot explores whether these functionalities impact on the patients' health-related quality of lives (HRQoL) and needs in cancer supportive care. It also aims to assess whether it improves the burden on caregivers and the satisfaction with the use of the app. Finally, the cost-effectiveness of LuCApp will be explored, based on the improvement in HRQoL and the resources being used to manage the disease throughout the study period.

A number of outcome measures have been identified to allow the assessment of the above trial objectives. LuCApp will be evaluated in terms of: (1) impact on HRQoL, (2) impact on cancer supportive care needs, (3) impact on the burden for caregivers, (4) resource use, (5) usability and satisfaction with LuCApp. The rationale for selecting these measures and their characteristics are summarized in the next sections.

(1) HRQoL

The impact on HRQoL of using LuCApp will be measured with existing valid and reliable patient-reported outcome measures (PROMs). Their selection was based on the availability of a validated Italian version, for self-report use, that can be administered both on paper and via smartphones or tablets, and commonly used in lung cancer patients.

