except that the wording of the items does not refer to a usability-testing situation but is rather appropriate for a field-testing situation. The CSUQ was later adapted for mobile apps usability testing to elicit participant satisfaction with the PAediatric Risk Assessment (PARA) app, a mHealth tool developed to help health care professionals in resource-limited settings detect patients at high risk of both in-hospital and post-discharge mortality (48). Based on this revised version, the questionnaire was further elaborated upon: the final version consists of 12 items evaluated on a Likert scale ranging from 1 (“Strongly agree”) to 7 (“Strongly Disagree”). In addition, three qualitative questions were added to draw further information on the application and on the generalizability of LuCApp in the current and other clinical contexts: 1) “What do you like the most about the App?”; 2) “What do you like the least about the App”; 3) “How could the App be changed to make it easier to use?”. No validated Italian version of the CSUQ was available, so the authors, in cooperation with healthcare professionals of the participating sites, developed the current version. The questionnaire will be administered at the end of the study.

(5) Resource use

The perspective taken for the evaluation of resource consumption will be that of the National Healthcare System. In order not to overload patients and the App design with additional modules, resource use will be captured through patients reports of symptoms and clinicians actions in response to those symptoms (e.g. prescriptions, hospitalization, change in therapy). Moreover, additional information will be obtained for both control and treatment group patients via a form administered by the physician during the clinics. Unitary costs will be expressed as euros 2018. Drug unitary costs will be derived from national price listings, laboratory and instrumental tests will be valued according to the outpatient procedures formulary in accordance with the ongoing policies of Lombardy Region as well as eventual hospitalizations.

Figure 6 summarizes the data collection process throughout the study.

Figure 6 - Time-points of outcomes assessment

Sample size

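### Costs are compared by unadjusted tests although randomisation is stratified by therapy and centre; to the extent that these predict cost, precision on an exploratory outcome is given away

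*Combined protocol and SAP*

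**What the plan says.** **Randomization.** Allocation uses "randomly permuted blocks and stratified by trial centers and therapy", the therapies being chemotherapy, immunotherapy and biological therapy. With three centres this makes up to nine strata.

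**Statistical methods.** Costs get one sentence: "Resource consumption and related costs will be calculated and reported for each treatment group and compared by means of parametric and non-parametric tests (52"; nothing further is specified. The sentence just before treats QALYs differently: "A multivariable linear regression model with QALY as dependent variable will be used to adjust for other covariates". FACT-L change also gets an adjusted regression and survival an adjusted Cox model. EQ-5D-5L, FACT-L and HADS get repeated-measures and mixed models that allow for centre. The therapy stratum is not named in any of these models.

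**Outcomes, (5) Resource use.** The perspective is that of the national health system. Resource use comes from symptom reports and "clinicians actions in response to those symptoms (e.g. prescriptions, hospitalization, change in therapy", plus a physician-completed form in both arms whose content is not described. On valuation: "Drug unitary costs will be derived from national price listings".

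**Status of the question.** The opening of Outcomes says that "the cost-effectiveness of LuCApp will be explored". No cost SD, target difference or power is given. The significance rule in Statistical methods makes no exception for costs: "Two-sided P values of less than .05 were considered to indicate statistical significance".

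**The concern.** When allocation is balanced within a factor that predicts the outcome, chance differences in that factor contribute almost nothing to the difference between arms. An analysis that ignores the factor still leaves its variation in the standard error. The reported uncertainty then exceeds the real sampling variation, and the test rejects less often than its nominal 5% under the null.

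For costs, the practical result is that a real difference in either direction is somewhat more likely to be reported as not significant. Any cost-effectiveness estimate built on the same mean difference inherits the imprecision. As planned, the two halves of that estimate would also be analysed differently, with QALYs adjusted and costs not.

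**Working it through.** **1. The plan's own figure.** The only sample size calculation for which a total is stated concerns the TOI: a 6-point difference and SD 11.54, with two-sided 5% and 80% power. Per arm, n = 2 × (1.96 + 0.84)² × (11.54/6)², which gives 59 (118 in total). The t-based value is 59.05, rounded up to 60 (120 in total). The stated 120 is reproduced. There is no corresponding figure for costs to check.

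**2. Formulae.** Let R² be the share of cost variance explained by the strata. It is an assumption throughout. With allocation balanced within strata:

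- true SE of the difference = unadjusted SE × √(1 − R²), so the interval that goes with the t-test is too wide by a factor 1/√(1 − R²);
- true type I error of the unadjusted test = 2 × [1 − Φ(1.96/√(1 − R²))];
- unadjusted power = Φ((2.80 − 1.96)/√(1 − R²));
- adjusted power = Φ(2.80/√(1 − R²) − 1.96).

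Here 2.80 is the standardised difference that the ordinary formula would credit with 80% power. At 60 per arm that is 2.80 × √(2/60) = 0.51 SD.

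**3. Results.**

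| Assumed R² | Interval too wide by | True type I error, unadjusted | Power unadjusted | Power adjusted |
|---|---|---|---|---|
| 0 | 0% | 5.0% | 80% | 80% |
| 0.1 | 5% | 3.9% | 81% | 84% |
| 0.2 | 12% | 2.8% | 83% | 88% |
| 0.3 | 20% | 1.9% | 84% | 92% |
| 0.5 | 41% | 0.6% | 88% | 98% |

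Worked line for R² = 0.3: √0.7 = 0.837 and 1/0.837 = 1.195. The unadjusted power is Φ(0.84/0.837) = 84%, and the adjusted power is Φ(2.80/0.837 − 1.96) = 92%.

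**4. Simulation at 120 patients.** Assumptions: nine strata, blocks of 4, therapy mix 50/35/15%, gamma-distributed costs. A Welch t-test was compared with regression on arm and therapy with robust SE.

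- No therapy effect: mean t-test SE 0.109, actual sampling SD 0.109.
- R² about 0.22: SE 0.195 against 0.174 (12% too large), null rejection 2.6%, power 83% v 89%.
- R² about 0.42: SE 0.420 against 0.327 (28% too large), null rejection 1.0%, power 85% v 94%.

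Across all scenarios run, including one at R² about 0.62, the adjusted test rejected a true null 4.4% to 5.4% of the time.

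**5. Sensitivity at 156 patients, with centre also in the model.** Assumptions: three equal therapy groups, blocks of 4, gamma costs. Here R² follows from the assumed ratios of mean cost and the within-therapy coefficient of variation (CV). For ratios 1:2:3 and CV 0.5, R² = 0.667/(0.667 + 0.25 × 4.667) = 0.36.

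| Mean-cost ratios | CV | R² | Power unadjusted v adjusted |
|---|---|---|---|
| 1:2:3 | 0.5 | 0.36 | 83% v 92% |
| 1:2:3 | 1.2 | 0.09 | 81% v 84% |
| 1:1.5:2 | 0.8 | 0.10 | 80% v 83% |
| 1:1.5:2 | 1.2 | 0.05 | 80% v 81% |

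With ratios 1:1.2:1.4 the gain was 0 to 2 points at any CV tried. Random loss of 30% of patients weakens the balance within strata: for ratios 1:1.5:2 and CV 0.5, the unadjusted type I error moved from 2.6% to 3.7%.

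**The case against.** **The premise is not documented.** A reader might infer that therapy class largely fixes each patient's cost, and that the cost comparison is therefore badly underpowered. The documents do not support that. The resource-use section centres on symptoms and the clinical response to them. A list-price rule says how drugs are valued, not whether the planned anticancer regimen is counted. If only symptom-driven use is costed, therapy may explain little. Hospital stays and variable time on study would also add spread within each therapy and lower R². This stands, and it is why the size can only be given as a range that starts at zero.

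**No stated target is missed.** Cost is exploratory, in a trial that the Discussion calls a pilot. Unadjusted power is never below the 80% reference in the scenarios above, so what is lost is a gain that could have been had. The plan also names no confidence interval for the cost difference; the excess width belongs to the interval that a t-test would produce. All of this stands.

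**The contrast with QALYs is limited.** The QALY and FACT-L regressions do not list their covariates, so the therapy stratum may be missing there too. That is correct. It is a reason to name the stratification terms in the QALY model as well, not to leave them out for costs.

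**A rank test is also planned.** With skewed costs and a constant shift, a Mann-Whitney test rejected more often than the adjusted regression (96% v 89% at R² about 0.22). The power figures here therefore concern the comparison of means only. A rank test does not estimate the mean difference that cost-effectiveness needs, and it too was conservative under the null (2.2% in that scenario).

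**Conclusion.** The point holds as an efficiency improvement on an exploratory outcome. The planned cost comparison ignores the factors used to balance the arms. If therapy or centre predicts cost at all, the unadjusted standard error is too large and the test is conservative. A reader might infer bias in the cost difference or an excess of false positives; neither follows, because the error runs in the cautious direction.

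The direction depends only on R² being above zero and on allocation being roughly balanced within strata. The size rests entirely on assumed inputs. In the sensitivity runs at 156 patients the gain in power was about 0 to 9 points, and attrition reduces it. A material gain is likely if anticancer drugs are part of the costed resources, and the protocol should say whether they are.

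**What to change.** In Statistical methods, make the main cost comparison a linear regression of total cost per patient on arm, therapy stratum as randomised and centre, reporting the adjusted difference in mean cost with a robust or stratified-bootstrap 95% confidence interval. Name the same stratification terms in the QALY model. Keep unadjusted mean costs by arm as description. In the resource-use section, state whether planned anticancer drugs are included in the drug costs.

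The cost is a sentence or two of wording and one regression. Therapy and centre are already known for every patient at randomisation, so no new data or patients are needed. The model uses four extra degrees of freedom (two for therapy, two for centre). If the strata turn out not to predict cost, almost nothing is lost, and fixing the terms now prevents a choice of covariates after the costs have been seen.

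### Cost-effectiveness is a stated aim, but costs and QALYs are only tested separately, so no joint estimate with uncertainty is planned and no cost estimand is named

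*Combined protocol and SAP*

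**What the plan says.** The opening of the Outcomes section sets the aim: "Finally, the cost-effectiveness of LuCApp will be explored, based on the improvement in HRQoL and the resources being used to manage the disease". Two later parts of that section supply ingredients:

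- Under EQ-5D-5L, the instrument is described as the usual tool to "derive utility values that can be utilized within an economic evaluation model".
- Under Resource use: "The perspective taken for the evaluation of resource consumption will be that of the National Healthcare System". The same paragraph fixes 2018 euros and the sources of unit costs.

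The analysis itself is in Statistical methods. QALYs are to be "compared using two group t-tests between LuCApp and standard care arm", and then: "A multivariable linear regression model with QALY as dependent variable will be used to adjust for other covariates". For costs there is one sentence: resource use and its costs are given by arm and "compared by means of parametric and non-parametric tests (52", where 52 is a reference on how to analyse cost data in pragmatic randomised trials. All results are judged at a two-sided 0.05 level.

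**The concern.** Cost-effectiveness is a question about two outcomes at once: how much extra is spent, and how much extra health it buys. Two separate tests do not answer it. Both can be non-significant while the data still say something useful about net benefit, and the precision of net benefit depends on how cost and QALY are correlated within patients, which separate tests ignore.

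The cost sentence adds a second gap. It names no estimand, no specific test, no leading test and no rule for disagreement. A health service pays the total bill, which is the number of patients times the arithmetic mean cost. A test of mean cost addresses that. A rank test addresses whether patients in one arm tend to cost less than patients in the other, which with skewed costs is a different question.

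At stake is whether this pilot's economic output can inform a later evaluation, and whether its cost conclusion refers to the quantity the chosen perspective needs.

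**Working it through.** **1. What the plan provides for each element of an economic comparison**

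- Incremental QALYs: t-test, plus a covariate-adjusted linear model.
- Incremental cost: arm-level reporting plus unnamed tests. No adjusted model, and no statement that the mean difference is the target.
- Incremental cost-effectiveness ratio or net benefit: none.
- Willingness-to-pay range: none.
- Joint uncertainty of cost and QALY: none.

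This part of the point needs no assumption.

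**2. Arm sizes for the illustrations**

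The plan gives no figure for costs or QALYs, so its only usable numbers are the arm sizes. Sample size states 120 evaluable for a 6-point TOI difference with SD 11.54. Check: n per arm = 2 × (1.960 + 0.842)² × (11.54/6)² = 2 × 7.85 × 3.70 = 58.1, so 59 per arm. The t-based calculation gives 59.05, so 60 per arm, or 120 in all, which reproduces the plan. Enrolment is 156, or 78 per arm. I use 60 and 78.

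**3. Why two separate tests do not answer the joint question** (all inputs assumed)

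Take 60 per arm, a mean cost difference of 500 euros (SD 8,000) and a mean QALY difference of 0.02 (SD 0.12).

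- QALY test: SE = 0.12 × √(2/60) = 0.0219, z = 0.91, p = 0.36.
- Cost test: SE = 8,000 × √(2/60) = 1,461, z = 0.34, p = 0.73.
- Ratio: 500 / 0.02 = 25,000 euros per QALY.
- Incremental net benefit at willingness to pay λ is 0.02λ − 500: −100 at 20,000, +100 at 30,000 and +300 at 40,000 euros.
- Its SE is √{(2/60) × [(0.12λ)² + 8,000² − 2ρ(0.12λ)(8,000)]}. At λ = 30,000 this is 1,878, 1,602 or 1,267 for a cost-QALY correlation ρ of −0.5, 0 or +0.5.

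The planned output would be the two p-values. The sign of net benefit depends on λ and its precision on ρ; the plan uses neither.

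**4. What a rank test would do, if one were used** (all inputs assumed)

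Costs are log-normal with a true mean of 5,000 euros in both arms. The median is 5,000 × exp(−s²/2), with s the log-SD. At s = 0.8 it is 3,631, at 1.0 it is 3,033 and at 1.2 it is 2,434. Unequal spread with equal means therefore forces unequal medians, which a rank test detects. Simulated rejection rates at two-sided 0.05, with 60 to 78 per arm:

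| Log-SD, arm 1 vs arm 2 | Rank test |
|---|---|
| Equal (0.8/0.8 or 1.0/1.0) | about 5% |
| 0.8 vs 0.9 | 8-10% |
| 0.8 vs 1.0 | 19-23% |
| 0.8 vs 1.2 | 53-66% |

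The Welch test of means stays at about 4-7% throughout. Direction can differ too. With log-SD 0.8 vs 1.2, a control median of 6,000 euros and a LuCApp median 20% lower, mean cost is 8,263 on control and 9,861 on LuCApp (1,599 higher before rounding), yet a LuCApp patient costs less than a control patient with probability 0.56.

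**5. Two tests without a lead**

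With identical cost distributions and 60 per arm, calling a difference when either test has p < 0.05 gives a type I error of about 7% instead of 5%.

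**The case against.** The strongest reply concerns the cost test. The plan says non-parametric, not rank. A bootstrap or permutation test of mean cost is also non-parametric and would not have the problem in step 4. The cited reference cannot be consulted here, so it settles nothing either way. This stands: a reader might infer that a rank test is planned and that the trial will mislead on cost, but the documents do not say so. What they leave is an unnamed test.

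The larger percentages also rest on unequal spread. With equal spread the rank test holds its 5%. The 0.8 vs 1.2 case implies SDs of about 4,734 and 8,973 euros at the same mean, and nothing in the documents predicts that. Unequal spread is conceivable, since alerts that can lead to hospital referral or medication changes exist only in the LuCApp arm, but it is not shown. A rank test that rejects there is detecting a real difference in medians; it misleads only if read as a statement about means.

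A reader might also infer that the authors could report whichever cost result suits, or that nothing could be said about cost-effectiveness. Neither follows. The text has costs reported by arm and compared by both kinds of test, and a crude ratio could be formed from arm means. It would be unplanned and without an interval.

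Finally, the study calls itself a pilot and the economic aim is only to be explored. That lowers the weight of the point but does not remove it: exploration calls for estimates with intervals more than for tests at 0.05.

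**Conclusion.** The point holds, chiefly as an omission. The Outcomes section poses a cost-effectiveness question and sets up its inputs; Statistical methods stops at two unconnected comparisons, so no incremental cost-effectiveness or net-benefit estimate with uncertainty is planned. This rests on reading the document alone.

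The cost-test half is an ambiguity: no estimand, no named test, no lead. Its possible size runs from nothing (equal spread, or a non-parametric method aimed at means) to a rank test rejecting in over half of trials with equal true means (log-SD 0.8 vs 1.2). The documents give no cost mean, SD or skew with which to place the trial in that range, so none of these percentages is a forecast.

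The primary TOI comparison is unaffected. The change should be made, but it has low urgency.

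**What to change.** Replace the cost sentence in Statistical methods with text to this effect:

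- The leading cost comparison is the difference in arithmetic mean cost between arms with a 95% CI. Bootstrap, Welch or regression-based intervals would each serve; name one. Any rank test or median is descriptive.
- Incremental cost and incremental QALYs are estimated jointly by patient, for example by resampling each patient's cost and QALY as a pair or by bivariate regression. The same covariates are used for both, such as baseline EQ-5D, centre and therapy (the last two are the randomization strata).
- Incremental net benefit is reported with a CI over a range of willingness-to-pay values stated before analysis, and labelled exploratory.

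The cost is a little more analysis on data already collected. If the authors already intended a bootstrap of mean cost, the first item is only a clarification.
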